6.1.8. Contraception

Within this study, all FCBP must have a negative pregnancy test ≤ 7 days prior initiation of study treatment. A FCBP is defined as any female who does not meet the criteria of non-childbearing potential. These are as follows:

- documented hysterectomy, bilateral oophorectomy (ovarectomy), or bilateral tubal ligation
- post-menopausal (a practical definition accepts menopause ≥ 1 year without menses with an appropriate clinical profile, e.g. age > 45 years in the absence of hormone replacement therapy (HRT). In questionable cases, the subject must have a follicle stimulating hormone (FSH) value > 40 mIU/ml and an estradiol value < 40 pg/ml.

Sexually active men and women of child-bearing potential must use two methods of reliable contraception including one highly effective (Pearl Index < 1) and one additional effective (barrier) method as described below maintained for up to 3 months after the last dose of study therapy.

The following contraceptive methods with a Pearl Index < 1 are regarded as highly-effective:

- oral hormonal contraception ('pill')

Please note: in case that its efficacy is impaired during the trial, e.g. due to vomiting and diarrhoea, additional/other methods as listed below are required to assure adequate safety

- dermal hormonal contraception/contraceptive plaster
- vaginal hormonal contraception (NuvaRing®)
- long-acting injectable contraceptives/implants that release progesterone (Implanon®)
- tubal ligation (female sterilization)
- intrauterine devices that release hormones (hormone spiral)
- double barrier methods
- partner's vasectomy

Additional effective (barrier) methods are:

- male condom
- diaphragm/cervical cap

The following contraceptive methods are not regarded as safe: condom plus spermicide, simple barrier methods (vaginal pessaries, condom, female condoms), copper spirals, rhythm/basal temperature method and withdrawal method (coitus interruptus).

6.2. Vaccination Phase

Vaccination phase begins as soon as possible (within 7 days) after screening and confirmation of patient's eligibility. If screening takes more than 48 hours, throat/nose swab for SARS-CoV-2 infection must be repeated. The vaccine can only be applied if a negative SARS-CoV-2 PCR test is available on the day of vaccination not older than 48 hours.

Peptide vaccines should be injected into the skin at the lower part of the abdomen of the patients. The site of vaccination (right or left) will be determined by the investigator and documented.

To minimize the risk for severe and unexpected side effects for subjects included in the study, all participants will be monitored for at least two hours after vaccination, including close monitoring of heart rate, blood pressure, temperature, oxygen saturation and subjective well-being. Each monitoring unit must be equipped with a crash cart and an intensive care team should be on standby.

Treatment and monitoring of the first volunteer are performed in an in-patient setting with access to intensive care for 24h. Close monitoring (every 30 minutes vital parameters) will be performed for the first four hours after vaccination. Thereafter, monitoring is performed at hourly intervals until 6 hours after vaccination. Thereafter every 3 hours until 24 hours after application of the vaccine.

6.2.1. Visit 1 (Vaccination) (Day 1)

- Signs/symptoms, baseline
- Vital signs, close monitoring after vaccination (blood pressure, temperature, heart rate and oxygen saturation every 30 minutes for at least 2 hours)
- Physical examination, baseline
- Assessment of concomitant medications

Protocol		
Protocol code and Short Title:	P-pVAC-SARS-CoV-2	Date/Version:08.03.2021/V1.4

- AE assessment
- Hematology and blood chemistry (local lab), approximately 10 ml blood
- Vaccination (section 5.7)
- T-cell response, baseline obtained before vaccination, approximately 60 ml blood
- Serological response, baseline obtained before vaccination, approximately 15 ml blood

6.2.2. *Visit 2 (Day 7 +/- 1)*

- Signs/symptoms, as assessed on volunteer's diary and visit
- Vital signs,
- Physical examination, including investigation of vaccination side
- Assessment of concomitant medications
- AE assessment
- Hematology and blood chemistry (local lab), approximately 10 ml blood
- T-cell response, approximately 60 ml blood
- Serological response, approximately 15 ml blood

6.2.3. *Visit 3 (Day 14 +/- 1)*

- Signs/symptoms, as assessed on volunteer's diary and visit
- Vital signs,
- Physical examination, including investigation of vaccination side
- Assessment of concomitant medications
- AE assessment
- Hematology and blood chemistry (local lab), approximately 10 ml blood
- T-cell response, approximately 60 ml blood
- Serological response, approximately 15 ml blood

6.2.4. *Visit 4 (Interim safety) (Day 28 +/- 2)*

- Signs/symptoms, as assessed on volunteer's diary and visit
- Vital signs,
- Physical examination, including investigation of vaccination side

Protocol		
Protocol code and Short Title:	P-pVAC-SARS-CoV-2	Date/Version:08.03.2021/V1.4

- Assessment of concomitant medications
- AE assessment
- Hematology and blood chemistry (local lab), approximately 10 ml blood
- T-cell response, approximately 60 ml blood
- Serological response, approximately 15 ml blood

6.2.5. *Visit 5 (End of Safety follow-up = EOSf)*

- Signs/symptoms, as assessed on volunteer's diary and visit
- Vital signs,
- Physical examination, including investigation of vaccination side
- Assessment of concomitant medications
- AE assessments
- Hematology and blood chemistry (local lab), approximately 10 ml blood
- T-cell response, approximately 60 ml blood
- Serological response, approximately 15 ml blood

6.2.6. *Visit 6-7 (Follow-up) (Month 3 and 6 +/- 7 days)*

- Medical history, anamnestic evaluation of SARS-CoV-2 specific symptoms
- T-cell response, approximately 60 ml blood
- Serological response, approximately 15 ml blood

6.2.7. *Volunteer's diary/card*

Each patient included in the P-pVac-SARS-CoV-2 study will receive a volunteer's card, which states that he/she is participating in the study (Appendix 13.4). This will also include a 24h emergency contact number. Furthermore, each patient will be provided with a volunteer's diary to note their symptoms daily (Appendix 13.3)

6.2.8. *Unscheduled Visit*

Subjects may contact the investigator at any time for an unscheduled phone or on-site visit should they experience clinical symptoms or signs following injection. At all unscheduled visits, the following minimum assessment will be performed: Questions concerning the history of the present illness as well as the subject's general health and lifestyle. Findings resulting in (S)AEs

Protocol		
Protocol code and Short Title:	P-pVAC-SARS-CoV-2	Date/Version:08.03.2021/V1.4

will be documented and reported as indicated. All other symptoms/signs will be reported on the next scheduled visit on eCRF.

Upon occurrence of symptoms characteristic of SARS-CoV-2 (i. e. cough, fever (cut-off $>39^{\circ}\text{C}$), loss of taste and smell, limb pain) at any time until day 56, subjects are supposed to get in touch with the investigator. Investigator will initiate SARS-CoV-2 testing for the volunteer (nose or mouth swab followed by PCR per institutional guidelines). If the test is positive, patients should be treated per investigators discretion. Positive results must be recorded as an AESI (section 9.1.4). Negative results will be followed by a second testing $\geq 24\text{h}$ later. Only upon the second negative test, patients are considered negative, all others must be reported as positive.

If participants are positively tested for SARS-CoV-2, all accompanying symptoms and treatments (e.g. hospitalisation, ICU) are recorded

Medically attended AEs and all SAEs will be recorded, and concomitant medication or vaccination will be noted. After identifying the history of the present illness and performing corresponding exams or laboratory tests, the investigator will decide on the best course of treatment according to standard medical practice.

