Length of Study/ Time Lines	
Total trial duration: 1 years
 
Duration for individual patient: Safety follow-up: 8 weeks
 
Follow-up: 4 months
 
Number of visits: 8
 
FSI (First Subject In): Q4/2020
 
LSI (Last Subject In): Q1/2021
 
LSO (Last Subject Out): Q3/2021
 
DBL (Data Base Lock): Q3/2021
 
Statistical Analyses Completed: Q4/2021
 
Trial Report Completed: Q4/2021
	

Table 1: Table of Events

Protocol activities and forms to be completed	Screening		Vaccination phase ¹				Follow-up period ²
						Interim Safety	
	≤ - 7 days	Day 1	Day 7 +/- 1 days	Day 14 +/- 1 days	Day 28 +/- 2 days	Day 56 +/- 2 days	3 and 6 months after peptide vaccination
Visit		V1	V2	V3	V4	V5	V6-7
Informed consent ³	X						
Demographics ⁴	X						
Medical history ⁵	X						X
Signs/symptoms ⁶		X	X	X	X	X	
Enrolment ⁷	X						
Clinical assessments							
Vital signs ⁸	X	X	X	X	X		
Physical examination ⁹	X	X	X	X	X		
Assessment of concomitant medications ¹⁰	X	X	X	X	X	X	
AE assessments ¹¹		X	X	X	X	X	X
Laboratory assessments							
Hematology (local lab) ¹²	X	X	X	X	X	X	
Blood chemistry and coagulation (local lab) ¹³	X	X	X	X	X	X	
Immunoglobulins/Immuno phenotype ¹⁴	X						
Urine analysis (local lab) ¹⁵	X						
HBV, HCV, HIV-1, (local lab) ¹⁶	X						
Pregnancy test ¹⁷	X						
SARS-CoV-2 testing	X ¹⁸						
Treatment							
Vaccine CoVac-1 ¹⁹		X					
Efficacy assessment							
T-cell response ²⁰		X	X	X	X	X	X
Serological response ²¹		X	X	X	X	X	X

Detailed information on schedule and activities are described in the footnotes.

1. The peptide vaccination should be applied as early as possible after screening (max. 7 days) and approved eligibility of the volunteer. Vaccination phase will be 2 months and ends with the end of safety follow-up (EOSf).
2. Follow-up: After vaccination phase, volunteers will enter follow-up, which ends with the last visit 6 months after vaccination (V7, EOS).
3. Informed consent and volunteer registration: every volunteer must date and sign informed consent form to participate in this trial before starting any trial-related procedures.
4. Demographics: gender, year of birth, ethnicity
5. Medical history: The investigator has to collect information on the volunteers' medical history including prior illnesses, hospitalisations, and symptoms of a SARS-CoV-2 infection.

Protocol		
Protocol code and Short Title:	P-pVAC-SARS-CoV-2	Date/Version:08.03.2021/V1.4

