- Granuloma formation at the vaccination site was also reported, albeit rarely, in subjects after BNT162b2 vaccination. In contrast to CoVac-1 induced granulomas, these local reactions were indeed reported to affect subject's daily life and also required specific treatment (e.g. steroids)⁹⁷.

Vaccine design and immunogenicity

- In contrast to approved vaccine candidates, the peptide-based CoVac-1 vaccine includes validated SARS-CoV-2 T cell epitopes that were proven (i) to be frequently detected in convalescents after natural SARS-CoV-2 infection, (ii) to be of pathophysiological relevance for T cell immunity to combat COVID-19 and (iii) to mediate long-term immunity after infection. Thus, CoVac-1 is expected to induce strong and long-lasting SARS-CoV-2 T cell immunity that is comparable to T cell immunity after natural infection.
- In contrast to approved vaccine candidates that induce immune responses limited to the spike protein of SARS-CoV-2, CoVac-1 induces broad T cell immunity targeting multiple viral proteins (e.g. spike, nucleocapsid, membrane, envelope etc.). This is of particular importance in light of emerging mutations that challenge efficacy of current vaccines.

Protocol		
Protocol code and Short Title:	P-pVAC-SARS-CoV-2	Date/Version:08.03.2021/V1.4

- In contrast to approved vaccine candidates that require two vaccinations, CoVac-1 induces strong T cell responses after one single vaccination.
- CoVac-1 induces earlier and stronger SARS-CoV-2 T cell responses after one single vaccination compared to the approved vaccine candidates. The detailed comparison of vaccine-induced SARS-CoV-2 T cell responses is provided in the IB section 6.2.

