2.3.1. Exploratory Endpoints

- Characteristics of T-cell response on Visits 2, 3, 4, 5 measured by ELISpot/ICS. This includes:
 - Phenotyping of SARS-CoV-2 specific T-cells (CD4, CD8 etc.) by flow cytometry
 - Characterization of cytokine profiles of SARS-CoV-2 specific T cells (TNF, IFN, IL-2, CD107a etc.) by intracellular cytokine staining
 - Recognition rate defined as percentage of peptides inducing a T cell response in one individual
 - Intensity of T cell response to a single SARS-CoV-2 T cell epitope included in the CoVac-1 vaccine
- Induction of long-term SARS-CoV-2 specific T-cell responses 3 and 6 months after peptide vaccination.
- Induction of antibodies specific to the SARS-CoV-2 T-cell epitopes included in the CoVac-1 vaccine measured by ELISA. In case of unexpected detection of CoVac-1 specific antibodies the following assays will be performed:
 - Individual neutralization antibody titers
 - Seroconversion rates
 - Calculation of geometric mean titers (GMT) for neutralizing and binding antibodies
- Biomarkers and clinical characteristics influencing immunogenicity.

Protocol		
Protocol code and Short Title:	P-pVAC-SARS-CoV-2	Date/Version:08.03.2021/V1.4

3. Study Design

This is an interventional, open-label, phase I trial evaluating the CoVac-1 vaccine, a single dose SARS-CoV-2 specific multi-peptide vaccine combined with the TLR1/2 ligand XS15 emulsified in Montanide ISA 51 VG in adults. The study is divided into two parts, which will recruit consecutively. Prior to initiation of the next part, the previous part must have completed recruiting, and day 28 of the last patient enrolled must have passed. After interim safety analysis and approval from the authorities (section 9.5), the next study part starts recruiting (Figure 1 and 2).

The first volunteer included in the trial will be hospitalized after vaccination and closely monitored. This patient is observed until day 28 and possibly arising safety issues are reported to and decided on by the Sponsor. Thereafter, no more than one subject per day will be treated/vaccinated. 28 days following vaccination of the 12th volunteer, there will be an interim analysis of safety and a safety review by the data safety monitoring board (DSMB) as well as a substantial amendment to the regulatory authorities (PEI and EC) before proceeding to Part II. Part II must not start recruiting prior to approval by authorities. Volunteers of part II are treated simultaneously. Details can be found in figure 3.

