4.1.2. Exclusion Criteria

Subjects presenting with any of the following criteria will not be included in the trial:

1. Pregnant or lactating females.
2. Participation in any clinical study with intake of any investigational drug interfering with the study primary endpoint
3. Any concomitant disease affecting the effect of the therapeutic vaccine or interfering with the study primary endpoint
4. Any immunosuppressive treatment except low dose corticosteroids ($\leq 10\text{mg}$ prednisolone/day)
5. Prior or current infection with SARS-CoV-2 tested serologically or by throat/nose swab (PCR)
6. History of Guillain-Barré Syndrome
7. Positive serological HIV, hepatitis B or C test. In case of positive HBsAg, volunteer must provide prove of hepatitis B vaccination, otherwise volunteer must be excluded.
8. History of relevant CNS pathology or current relevant CNS pathology (e.g. seizure, paresis, aphasia, cerebrovascular ischemia/hemorrhage, severe brain injuries, dementia, Parkinson's disease, cerebellar disease, organic brain syndrome, psychosis, coordination or movement disorder, excluding febrile seizures as child)
9. Baseline laboratory with lymphocyte count $\leq 1000/\mu\text{l}$
10. Only Part I:
 - o Acute or chronic, clinically significant psychiatric, hematologic, pulmonary, cardiovascular, or hepatic or renal functional abnormality as determined by the

Protocol		
Protocol code and Short Title:	P-pVAC-SARS-CoV-2	Date/Version:08.03.2021/V1.4

Investigator based on medical history, physical exam, and/or laboratory screening test

11. All parts of the clinical trial

- Diabetes mellitus Typ II requiring drug treatment
- Chronic lung disease requiring drug treatment
- Any chronic liver disease or unknown liver abnormalities defined as:
 - ALT and AST $\leq 2.5 \times$ ULN
 - γ -GT $\leq 2.5 \times$ ULN
- Chronic renal failure defined as GFR $< 60 \text{ ml/min}/1,73\text{m}^2$
- Serious pre-existing cardiovascular disease such as NYHA $\geq I$, coronary heart disease requiring coronary surgery or known pAVK \geq grade 2
- Sickle cell anemia
- Obesity (as defined by age adjusted body mass index)

12. Hospitalization at study inclusion

13. Administration of immunoglobulins and/or any blood products within 120 days preceding study entry or planned administration during the study period

14. History of blood donation within 30 days of enrolment or planned donations within the study period

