The investigator will review all information obtained from the screening procedures via an eligibility form. The investigator will confirm, in writing, whether the subject fulfils all criteria for eligibility. Volunteers who fulfil all the inclusion criteria and none of the exclusion criteria will be eligible to participate in the trial. Screening failures, i.e. screened volunteers not in compliance with all criteria, are to be excluded and the reason will be recorded in the volunteer records. Information of volunteer's trial participation can be provided to the volunteer's general practitioner if the volunteer agrees.

6.1.3. *Enrolment*

A volunteer is considered for screening when he or she has signed the Informed Consent form.

In case of confirmation of volunteer's eligibility (volunteers must meet all inclusion criteria and must not meet any exclusion criteria), volunteer will be registered under a specific Vol. ID on a subjects log kept at the trial site. Only these volunteers are enrolled in the study, all others are assessed as screening failures.

The study is open-label.

6.1.4. *Randomisation*

No randomisation will be done in this clinical trial.

6.1.5. *Concomitant Medication and Treatments*

Relevant additional medications and treatments administered to the subjects on entry to the trial or at any time during the trial are regarded as concomitant medications and treatments and must be documented on the appropriate pages of the CRF.

6.1.6. *Permitted Prior and Concomitant Medications and Treatments*

The following concomitant medications and treatments are permitted during the trial.

Part I: No concomitant medication, apart from contraception for FCBP.

Part II : Any concomitant medication (already applied at screening) for e.g. other diseases are allowed except for medications stated in section 6.1.7.

6.1.7. *Prohibited Prior and Concomitant Medications and Treatments*

The following concomitant medications and treatments are prohibited during the trial:

Protocol		
Protocol code and Short Title:	P-pVAC-SARS-CoV-2	Date/Version:08.03.2021/V1.4

- Immunosuppressive agents apart from (≤ 10 mg prednisolone or equivalent)
- During the trial, other vaccinations or non-urgent medical interventions are prohibited. Initiation of new medications, regardless of indication must be discussed with the investigator and must be noted on the participant's record.

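### Visits 6-7 schedule no check for another COVID-19 vaccination, and the protocol does not say how month-3 and month-6 samples taken after one are analysed

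*Supplement*

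**What the plan says.** All references are to protocol V1.4 (08.03.2021).

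- **General rules.** Section 6.1.5 covers relevant treatments given "on entry to the trial or at any time during the trial are regarded as concomitant medications and treatments and must be documented" on the CRF. Section 6.1.7 states: "During the trial, other vaccinations or non-urgent medical interventions are prohibited". It also requires any new medication to be discussed with the investigator and noted. Under 6.10 a subject's study ends at the last visit, so these rules run to month 6.
- **Schedule.** Visits 1 to 5 (6.2.1 to 6.2.5) each list "Assessment of concomitant medications". Table 1 marks that row from screening to Visit 5 and leaves the Visit 6-7 column empty. Section 6.2.6 lists "Medical history, anamnestic evaluation of SARS-CoV-2 specific symptoms", a T-cell sample and a serology sample.
- **Endpoint.** Section 2.3.1 has as an exploratory endpoint: "Induction of long-term SARS-CoV-2 specific T-cell responses 3 and 6 months after peptide vaccination".
- **Other vaccines.** Section 1.3 refers to three vaccines already approved by the EMA. Section 1.1.5.3 sets CoVac-1 apart with the words "In contrast to approved vaccine candidates that induce immune responses limited to the spike protein of SARS-CoV-2". Table 3 names spike as the source protein of one of the six CoVac-1 peptides.
- **Entry.** Exclusion criterion 5 concerns prior or current infection. Neither the criteria nor the screening list in 6.1.2 names earlier COVID-19 vaccination.

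**The concern.** The trial sets a rule for the whole of each subject's participation, but its last scheduled check on that rule is at day 56. Part II enrols people aged 56 to 80, with last subject out planned for Q3/2021 and three other vaccines already approved. Outside vaccination before month 6 is foreseeable despite the ban.

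The month-3 and month-6 samples are the trial's only look at durability beyond day 56, and long-lasting T-cell immunity is part of the vaccine's stated aim (section 1.3). If a spike vaccine was given in between, a positive result on the spike-labelled peptide no longer shows that CoVac-1 immunity lasted. The protocol does not say what happens to such a sample. Section 6.6 does not make a prohibited vaccination a reason for ending participation, section 3 plans analysis by intention-to-treat, and sections 7.4.5 and 8.3 are silent on it. The sample would by default be pooled with the rest.

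**Working it through.** The plan gives no figure on this point, so the check is mainly a comparison of passages.

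**1. Does any scheduled step at Visits 6-7 ask about vaccination?**
- The concomitant-medication row of Table 1 has six marks, screening to Visit 5, and none at Visits 6-7.
- Medical history is marked at Visits 6-7. Footnote 5 of Table 1 defines it as prior illnesses, hospitalisations and symptoms of SARS-CoV-2 infection. Vaccination is not among them.
- Table 1 also marks AE assessment at Visits 6-7, but an uneventful vaccination is not an adverse event.
- Section 6.2.8 has vaccination noted at unscheduled visits, which take place only if a volunteer makes contact about symptoms.

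The answer is no. Taking six months as 182 days, the interval without a scheduled check is 182 − 56 = 126 days, and 126/182 = 69% of follow-up. This is a length of time, not an effect size, but both long-term samples fall at or within its end.

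**2. Does the assay separate the sources?**
Section 6.3.2 adds further SARS-CoV-2 epitopes to tell vaccine-induced responses from natural infection. It does not mention another vaccine. The additional serology in 6.3.2 is not described for that use either.

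**3. How much of the readout is exposed?**
One of six peptides is labelled spike: 1/6 = 17%. A spike-only vaccine could mimic a response to that peptide and not to the other five. In Part I the volunteers recognised 4 to 6 of the six peptides, median 5 (1.1.5.2). Each therefore recognised at least 4 − 1 = 3 non-spike peptides.

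**4. Illustration of the bias.**
Let *t* be the true long-term responder rate, *v* the share given another COVID-19 vaccine before the sample, and *s* the chance that it turns the spike-labelled peptide positive. If any one peptide counts, and vaccination is independent of true response,

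observed rate = *t* + (1 − *t*) × *v* × *s*.

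The documents give none of these inputs. With *v* assumed from 0.1 to 0.6 and *s* from 0.25 to 1.0:

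| True rate *t* | Lowest (*v*=0.1, *s*=0.25) | Highest (*v*=0.6, *s*=1.0) |
|---|---|---|
| 0.5 | 0.5 + 0.5×0.025 = 0.5125 | 0.5 + 0.5×0.6 = 0.80 |
| 0.8 | 0.8 + 0.2×0.025 = 0.805 | 0.8 + 0.2×0.6 = 0.92 |
| 1.0 | 1.0 | 1.0 |

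The bias vanishes when everyone still responds and grows as responses wane. The same formula applies to the spike-labelled peptide alone, with *t* as the persistence of that one response; there the other five peptides give no protection.

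**The case against.** The strongest reply is that the protocol already has the duty and the ban. Section 6.1.5 requires CRF documentation throughout, 6.1.7 prohibits other vaccinations, and 6.2.8 notes them at unscheduled contacts. This stands as far as it goes: a reader might infer that an outside vaccine goes unrecorded, and the documents do not support that. What is missing is a scheduled prompt after Visit 5 that makes the general rule work.

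Three other tempting inferences also fail.

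- *Immunosuppressants started after day 56 are lost in the same way.* Section 6.1.7 expressly requires new medications to be discussed with the investigator and noted, whatever the indication.
- *The secondary endpoint at Visits 2-5 is contaminated.* Concomitant medication is assessed at each of those visits, and 6.3.2 requires at least a two-fold rise over the volunteer's own Visit 1 value. A vaccine given after day 56 cannot affect them.
- *The spike-labelled peptide alone makes a month-6 responder.* The at-least-one-epitope wording belongs to the Visit 2-5 endpoint in 2.2.1. Section 2.3.1 gives no responder definition for months 3 and 6, so any-peptide scoring there is an assumption.

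It is also fair to say that per-peptide readouts would show whether the five non-spike responses persist, and that a breadth like Part I's would mask the problem if it lasted. Finally, no separate analysis plan is in the supplement, and a handling rule could be placed there. Such a rule would still need the vaccine and its date, which no scheduled visit after day 56 collects.

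**Conclusion.** The point holds as a mismatch between the rules in 6.1.5 and 6.1.7 and the Visit 6-7 schedule, together with the lack of a stated way to analyse month-3 and month-6 samples taken after another COVID-19 vaccine. Its reach is limited to exploratory long-term results. The primary safety endpoint and the Visit 2-5 secondary endpoint are not affected.

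The size depends on how far responses have waned. There is no distortion of an any-peptide rate that is truly 100%. A true 80% could read as 80.5-92% and a true 50% as 51-80%, under the assumed ranges for vaccination and spike reactivity. The number of samples affected cannot be stated, because the documents give no uptake figure and the trial prohibits the event.

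The conclusion takes two things from the protocol as given: that approved vaccines act on spike, and that Table 3's protein name for the peptide is right. The ORF entry in that row matches the nucleocapsid rows, so the label should be confirmed before it is used in a scoring rule.

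**What to change.** 1. Mark the concomitant-medication assessment at Visits 6-7 in Table 1 and add it to 6.2.6, with product and date of any COVID-19 vaccine.
2. Record any earlier COVID-19 vaccination at screening (6.1.2).
3. State in section 8 or the analysis plan that month-3 and month-6 T-cell and antibody results are reported with samples taken after another COVID-19 vaccine shown separately, or with T-cell responses scored without the spike-labelled peptide.

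The cost is one item at two existing visits, one screening question and one split of an exploratory table. The only loss is that the summary attributable to CoVac-1 may rest on fewer volunteers.
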